12.2.2 Safety

All safety data (scheduled and unscheduled) will be presented in the data listings.

Safety variables (ie, clinical laboratory values, vital signs, and ECGs) will be reported to the same precision as the source data. Derived variables will be reported using similar precision to those from which they were derived (eg, QT_c derived from QT interval).

Extra measurements (such as unscheduled or repeat assessments) will not be included in the descriptive statistics, but will be included in data listings. All AEs, ECG outliers, and clinical laboratory outliers that occur following the first dose of study medication will be included in the tabulations of AEs and outlier events, including episodes that occur at unscheduled evaluations.

All available data from subjects in the safety analysis set will be included in the safety analyses. No adjustment or imputation will be utilized for missing values or for subjects who withdraw prior to completing the study, neither will analyses be restricted to subjects with complete data.

All AEs will be collected for each subject when informed consent is obtained (Visit 1) until the follow-up visit (Visit 3). AEs that occur before dosing will be reported separately.

AEs will be summarized by preferred term and system organ class using MedDRA vocabulary (version 12.0 or higher) by treatment and across all treatments. Furthermore, listings of SAEs and AEs that led to withdrawal will be made and the number of subjects who had any AEs, SAEs, AEs that led to withdrawal, and AEs with severe intensity will be summarized.

Tabulations and listings of data for vital signs, clinical laboratory tests, ECGs, and physical examination findings will be presented. All continuous safety data will be summarized across all treatments for the absolute value at each scheduled assessment and for the corresponding change from baseline. For clinical laboratory tests, listings of values for each subject will be presented with abnormal or out-of-range values flagged. Clinical laboratory data will be reported in Système International units in the CSR.

For ECG parameters, the QT correction factor will be based on the Fridericia's formula. Further categorical summaries of absolute QT and QTcF values (greater than 450 ms, greater than 480 ms, greater than 500 ms) and change-from-baseline values in QT and QTcF values (greater than 30 ms, greater than 60 ms) may also be produced.

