For Groups 1 through 3 the duration of each subject's participation will be approximately 47 days, including a screening period of up to 30 days, a treatment period consisting of 6 to 7 nights (depending on the admission day) and a follow-up visit, 7 to 10 days after discharge from the treatment period.

For the first 4 subjects in Group 5 (Part 1) participating in the 2-period portion of the study, duration of each subject's participation will be approximately 55 days. These subjects will be given the option to remain at the clinic between samplings for the off dialysis assessment (post dialysis dosing) at the discretion of the Investigator.

For the remaining subjects in Group 5 (Part 2) participating in a single treatment period, duration of each subject's participation will be approximately 47 days.

Subjects may be admitted to the clinic on Day -2 for the Day -1 assessments at the discretion of the Investigator.

Outcome variable(s):

- Pharmacokinetic
 - Primary plasma pharmacokinetic parameters: AUC and C_{max},
 - Secondary plasma pharmacokinetic parameters: CL/F, t_{1/2}, t_{max}, and V_z/F in all subjects; Ae, CL_D, and fe in Groups 1 to 4; A_{d(4-8)}, Cl_R, and fd₍₄₋₈₎ in Group 5 during Period 2

- **Safety**

Adverse events and serious adverse events including severity, vital signs, physical examinations, laboratory parameters, electrocardiograms, and the Columbia-Suicide Severity Rating Scale.

Statistical methods

Tabulations and listings of data for vital signs, physical examinations, clinical laboratory tests, and electrocardiograms will be presented. Results from the Columbia Suicide Severity Rating Scale will be presented separately in a listing only. For clinical laboratory tests, listings of values for each subject will be presented with abnormal or out-of-range values flagged (other than those associated with renal impairment and /or stable chronic condition). Plasma and urine concentration data and the derived pharmacokinetic parameters will be summarized by renal function group using descriptive statistics.

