4.2 Exclusion criteria

Subjects should not enter the study if any of the following exclusion criteria are fulfilled:

1. History of any clinically significant medical, neurologic or psychiatric disease or disorder (other than those previously defined as acceptable for these population) which, in the opinion of the Investigator and sponsor, may either put the subject at risk because of participation in the study, or influence the results of the subject's ability to participate in the study: This includes seizure activity and repeated episodes of major depression.
2. Subjects with a history of suicide attempts in the past year and/or seen by the Investigator as having a significant history of risk of suicide or homicide, or considered at risk for suicide or homicide during the study.
3. History of gastrointestinal surgery (with the exception of cholecystectomy and appendectomy) or unintentional rapid weight loss.
4. Subjects with an active renal transplant (subjects who have previously received a renal transplant and are currently undergoing dialysis due to transplant failure may be enrolled)
5. Any clinically significant acute illness or medical/surgical procedure within 4 weeks of the first administration of investigational product (IP) (other than those previously defined as acceptable for these population) as judged by the Investigator.
6. Clinically significant progression of current disease or clinically relevant trauma, as judged by the Investigator, within 2 weeks before the first administration of the IP.

7. Any clinically significant abnormalities (other than those associated with the subject's degree of renal impairment and /or stable chronic condition) in clinical chemistry, hematology or urinalysis results as judged by the Investigator and Sponsor.
8. A positive result on screening for serum hepatitis B surface antigen or human immunodeficiency virus (HIV).
9. Clinically significant abnormal vital signs as judged by the Investigator
10. Any clinically important abnormalities in rhythm, conduction or morphology including abnormalities suggestive of acute changes or recurrent ischemic changes of resting electrocardiograms (ECG) as determined by the Investigator and sponsor
11. Prolonged QTcF (subjects with up to 500 ms prolongation are acceptable with joint approval with investigator and sponsor) or shortened QTcF (less 340 ms), or family history of Long QT Syndrome

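### ECG and laboratory outliers are tabulated on post-dose timing alone, so the counts mix abnormalities present before dosing with any drug effect

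*Supplement*

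**What the plan says.** **Outlier tabulation.** Protocol Section 12.2.2 leaves unscheduled and repeat measurements out of the descriptive statistics, then states: "All AEs, ECG outliers, and clinical laboratory outliers that occur following the first dose of study medication will be included in the tabulations". Episodes at unscheduled evaluations are included. Neither the term outlier nor a treatment-emergent condition is defined. Pre-dose AEs are reported separately; nothing similar is said for ECG or laboratory outliers.

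**Analyses that use the pre-dose value.** The same section summarises continuous safety data "for the absolute value at each scheduled assessment and for the corresponding change from baseline". Counts of subjects with absolute QT or QTcF above 450, 480 or 500 ms are optional. So are the change categories, of which the section says: "change-from-baseline values in QT and QTcF values (greater than 30 ms, greater than 60 ms) may also be produced". Section 11.1 sets the baseline at Day -1 for laboratory tests and Day 1 for ECG, separately for each period.

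**Eligibility.** Exclusion 7 excludes clinically significant laboratory abnormalities "other than those associated with the subject's degree of renal impairment and /or stable chronic condition". Exclusion 11, on prolonged QTcF, adds that "subjects with up to 500 ms prolongation are acceptable with joint approval with investigator and sponsor". Both apply to every group.

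**Flags in laboratory listings.** Section 12.2.2: "listings of values for each subject will be presented with abnormal or out-of-range values flagged", with no exemption. Synopsis, Statistical methods: "abnormal or out-of-range values flagged (other than those associated with renal impairment and /or stable chronic condition".

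**The concern.** A secondary objective (Section 2.2) compares safety and tolerability in impaired subjects with that in controls. The groups are defined by eGFR, which is computed from serum creatinine, so they differ in renal chemistry before any drug is given. A table that counts every out-of-range value after the first dose will show a gradient across groups even if TC-5214 does nothing. A real worsening in a subject who was already out of range adds nothing to the count. A subject admitted with a long QTcF enters the absolute QTcF rows in the same way.

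The flagging rules add a second difficulty. One flags every out-of-range value. The other leaves some unflagged on a judgement with no stated criterion, so a worsening of renal chemistry could go unmarked.

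**Working it through.** The plan states no figure on this point. The check has four steps.

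**1. Creatinine implied by the group limits.** Section 6.2 gives eGFR = 175 × Scr^-1.154 × age^-0.203 × (1.210 race factor, if it applies) × (0.742 if female). Solved for creatinine:

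Scr = [175 × age^-0.203 × sex factor × race factor / eGFR]^(1/1.154)

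| eGFR limit | Man, 60, race factor 1 | Woman, 60, race factor 1 | Range over ages 18-80, both sexes, both race factors |
|---|---|---|---|
| 80 (Groups 1/2) | 0.96 | 0.74 | 0.70-1.40 |
| 50 (Groups 2/3) | 1.44 | 1.11 | 1.06-2.10 |
| 30 (Group 3, Group 5) | 2.24 | 1.73 | 1.65-3.27 |

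(mg/dL)

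**2. Compare with a reference limit.** The documents give none. I assume an upper limit between 1.0 and 1.5 mg/dL, and a Day -1 creatinine close to the screening value used for classification.

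- Group 5 (eGFR below 30): creatinine is above 1.65 at every eligible age, sex and race factor, so it is out of range throughout the assumed limits.
- Group 3 (30 to below 50): at age 60 and race factor 1, a man is above 1.5 once eGFR is below 47.7, which covers most of the band. A woman is above 1.1 throughout the band (that limit corresponds to eGFR 50.7), but above 1.5 only when eGFR is below 35.4. A woman of 80 just under eGFR 50 has about 1.06, inside a limit of 1.1. So the result is most, not all, and it weakens for women if the limit is high.
- Group 1 (above 80): at age 60 and race factor 1, creatinine is below 0.96 (men) or 0.74 (women), in range throughout. With the 1.210 factor, a man just above eGFR 80 can reach about 1.21 at age 40 and 1.40 at age 18. So the result is few, not necessarily none.

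**3. Effect on a count out of 8.** Suppose there is no drug effect and a share q of a group is out of range before dosing and stays so. Expected count = 8q; chance of at least one = 1 - (1 - q)^8.

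| q | Expected count, rule as written | Chance of at least one | Treatment-emergent count |
|---|---|---|---|
| 0.25 | 2 | 0.90 | 0 |
| 0.50 | 4 | 0.996 | 0 |
| 1.00 | 8 | 1.00 | 0 |

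For QTcF, each subject admitted above a threshold who stays there adds 1/8 = 12.5 percentage points to that row. The documents do not say how many such subjects to expect.

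**4. Do the other analyses cover the gap?**

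- Laboratory: change from Day -1 is firmly planned, but unscheduled values are left out of descriptive statistics and enter only the outlier table and the listings.
- ECG: the categorical summaries are optional. Section 11.1 takes Day 1 as baseline, but footnote c of Tables 1 and 2 schedules ECGs at screening, Day -1, Day 1 at 4 hours postdose, discharge and follow-up. The only scheduled Day 1 ECG is postdose, so as written the change categories do not compare with a pre-dose recording.
- Group 5, Part 1 is dosed twice. Everything after the first dose includes the Day -1 values of Period 2, which Section 11.1 treats as that period's baseline.

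**The case against.** The best defence is that the quoted sentence is not meant to define an outlier. It makes sure that episodes at unscheduled visits are not lost, and an outlier that occurs after dosing could be read as one of new onset. No separate SAP is shown, and outlier criteria and shift tables are commonly left to one. The trial has 8 subjects per group and no formal testing, and all safety data are listed, so a reader can look up each Day -1 value. These points limit the consequence. They do not remove it: the protocol does state an inclusion rule, timing is its only condition, and the new-onset reading is not written down.

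Four stronger readings are tempting, and the documents do not support them.

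- A reader might infer that the safety analysis ignores the pre-dose value. It does not: laboratory change from baseline is planned, and QT/QTcF change categories are offered.
- A reader might infer that the outlier tables measure kidney disease instead of drug effect. They mix the two.
- A reader might infer that only the impaired groups are affected. Exclusions 7 and 11 apply to all groups, the synopsis exemption also covers stable chronic conditions, and Section 3.2 restricts controls to people who have such conditions.
- A reader might infer that the synopsis removes values from the analysis. It concerns flags in listings only.

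**Conclusion.** The point holds as a weakness in a stated secondary comparison; the primary pharmacokinetic analysis is untouched. As written, the ECG and laboratory outlier counts combine pre-existing abnormality with drug effect. For creatinine-type tests the baseline part could dominate: essentially all of Group 5 and most of Group 3 would be counted with no drug effect, against few controls. This rests on assumed upper limits of 1.0 to 1.5 mg/dL and on stable creatinine between screening and Day -1. A flat 8 of 8 against 0 of 8 should not be claimed, because both ends fail for some eligible combinations of age, sex, race factor and limit. For QTcF the mechanism is clear but its size cannot be computed. The mismatch between the synopsis and 12.2.2 on flags, and the ECG baseline without a pre-dose recording, follow from the text with no assumption.

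**What to change.** 1. In 12.2.2, count an ECG or laboratory outlier only if it is treatment-emergent: in range on that period's Day -1 and out of range postdose, or, if already out of range on Day -1, worsened by a prespecified amount. Keep unscheduled values in.
2. Add Day -1 to worst-postdose shift tables by renal group for QTcF (for example up to 450, 451-480, 481-500 and above 500 ms) and for key chemistries.
3. In 11.1, set the ECG baseline to the scheduled Day -1 recording of the period.
4. Reconcile the synopsis with 12.2.2: flag every out-of-range value, show the Day -1 flag beside it, and delete the exemption.

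For Group 5, Part 2, Table 2 places dialysis on Days 1 and 4, between the Day -1 and Day 6 chemistries. The prespecified amount, or a table footnote, should allow for dialysis timing.

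The cost is protocol and table-shell wording. No new visit, sample or recording is needed.

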12.2.3 Pharmacokinetics

Pharmacokinetic concentrations will be reported to the same precision as the source data. For descriptive statistics, concentrations below lower limit of quantitation (LLOQ) values will be handled as follows:

- At a time point where at least 1 value is above LLOQ, but less than or equal to 50% of values are below LLOQ, all values below LLOQ are set to LLOQ and a mean (arithmetic and geometric) value and SD and CV% are calculated
- At a time point where more than half of the observations are below LLOQ only individual values are reported; mean, SD, geometric mean and CV% will be set to NQ (non quantifiable). The min value and the median are set to less than LLOQ
- If all values are below LLOQ, at any time point, no descriptive statistics are calculated for that time point. Write NA (not applicable) in the field for SD and CV% and write less than LLOQ in fields for mean, geometric mean, min, median and max in the table
- The number of observations greater than LLOQ [number of observations above LLOQ (N greater than LLOQ)] will be reported in the table

Pharmacokinetic parameters will be rounded for reporting purposes in the summary tables and subject listings, as per [REDACTED] SOPs.

Data from subjects excluded from an analysis population will be included in the data listings, but not in the summaries.

Pharmacokinetic data will be presented by renal function group using the primary classification of eGFR determined by the MDRD formula. In addition, as supportive information, a tabular summary of PK parameters will be presented based on an estimate of their creatinine clearance (CL_{CR}) derived using the Cockcroft-Gault equation ([Cockcroft 1976](#)), using the following formulas:

For males:

$$- CL_{CR} \text{ (mL/min)} = \{[(140-\text{age}(\text{years})) \times \text{weight}(\text{kg})] / 72 \times \text{serum creatinine (mg/dL)}\}$$

For females:

$$- CL_{CR} \text{ (mL/min)} = \{[(140-\text{age}(\text{years})) \times \text{weight}(\text{kg})] / 72 \times \text{serum creatinine (mg/dL)} \times 0.85\}$$

A listing of PK blood sample collection times as well as derived sampling time deviations will be provided. A listing of all concentration-time data, individual and dose-normalized PK parameters will be presented by renal function. Figures of arithmetic mean concentration-time

data and dose-normalized PK parameters will be presented by renal function. Figures of PK parameters will also be presented by dose. Individual subject concentration-time data will be graphically presented on linear and semi-logarithmic scales.

For Groups 1 through 3 and Group 5, (Part 1, Treatment Period 1 and Part 2), regression models will be used to assess and quantify the relationship between renal function, as measured by eGFR, and TC-5214 dose-normalized primary pharmacokinetic parameters (C_{max} and AUC). The initial model will specify a linear relationship between primary pharmacokinetic parameters and eGFR and will be estimated using ordinary least squares. Log-transformations may be used to improve model fit. Non-linear models will be used if there is statistical evidence of departure from linearity at the 0.10 significance level. Further, models which are non-linear in the model parameters may be used if simpler models do not provide adequate fit. Model parameters, 90% CI and p-values will be reported. From the linear and final models, estimates of the mean pharmacokinetic parameters and 90% CI will be made at the median eGFR of each of the renal function groups, as will the differences (or ratios) and 90% CI relative to the normal renal group (at the group median eGFR).

As an exploratory analysis, the renal function groups will be compared using a one-way analysis of variance model on the log-transformed dose-normalized primary pharmacokinetic parameters (C_{max} and AUC). The renal impairment groups will be compared to the control subjects with normal renal function (Group 1), with the latter as reference. Geometric least-squares means with corresponding 95% CI and ratios of geometric least squares with corresponding 90% CI will be presented.

Comparisons of PK parameters for subjects in Group 5, Part 1, with ESRD between the two treatment periods (ie on a non dialysis day with those on a dialysis day) will be performed using a paired t-test (C_{max} and AUC).

